### 9.3.2. Outcomes

In both the SCRI and cohort studies, the pre-specified safety outcomes of interest will include the following:

- ADEM
- Anaphylaxis
- Bell's palsy
- CVST
- Convulsions/seizures (non-febrile)
- Encephalomyelitis
- Glomerulonephritis
- Guillain-Barré syndrome
- Herpes zoster
- Immune-mediated myositis
- Immune thrombocytopenia
- Kawasaki disease
- Multi inflammatory syndrome (in children and adults)
- MS
- MI
- Myocarditis/pericarditis
- PE
- Stroke, hemorrhagic
- Stroke, ischemic
- Transverse myelitis

In addition, in Phase 2 of the study, the following pregnancy outcomes will be assessed in pregnant women or their infants, if sample size permits:

- Spontaneous abortion
- Stillbirth
- Preterm birth
- Major congenital malformations
- Small for gestational age

Code lists for the safety outcomes of interest are provided in [Annex 2 \(Appendix III\)](#). Corresponding site of care requirements are listed in Table 2. When possible, outcomes will be defined using a validated claims-based algorithm with high performance ([CBER, 2021](#)).

If a safety signal is detected in the interim report, then medical records will be retrieved for a subset of participants to confirm the presence of that study outcome. A safety signal that requires confirmation through medical record review will be defined as a rate ratio of > 3.0 and a corresponding P value of < 0.01 in the primary analysis of the SCRI design (details in [Section 9.7.1.1](#)). Additionally, medical record review may be conducted for analyses beyond the primary SCRI analysis if a safety signal (defined as a rate ratio of > 3.0 and a corresponding P value of < 0.01) is detected in the interim or final report. Medical records may also be retrieved for AESIs with estimates approaching the pre-specified safety signal threshold.

**Table 2. Clean periods and risk intervals for safety outcomes of interest**

Outcome	Clean Period*	Vaccine Risk Interval*	Care Setting**
Acute disseminated encephalomyelitis	Days -28 to -1	Days 0 to 21	IP
Anaphylaxis	Days -30 to -1	Days 0 to 1	IP, ED
Bell's palsy	Days -183 to 0	Days 1 to 42	IP, OP
Cerebral venous sinus thrombosis	Days -365 to 0	Days 1 to 28	IP, OP
Convulsions/seizures, non-febrile	Days -42 to -1	Days 0 to 21	IP, OP
Encephalomyelitis	Days -183 to 0	Days 1 to 42	IP
Glomerulonephritis	Days -365 to 0***	Days 1 to 42***	IP, OP
Guillain-Barré syndrome	Days -365 to 0	Days 1 to 42	IP-primary position only
Herpes zoster	Days -270 to 0	Days 1 to 30	IP, OP
Immune-mediated myositis	Days -365 to 0***	Days 1 to 28	IP, OP
Immune thrombocytopenia	Days -365 to 0	Days 1 to 42	IP, OP
Kawasaki disease	Days -365 to 0	Days 1 to 21	IP, OP
Multi inflammatory syndrome	Days -365 to 0	Days 1 to 42	IP, ED
Multiple sclerosis	Days -365 to 0	Days 1 to 42***	IP, OP
Myocardial infarction	Days -365 to 0	Days 1 to 28	IP
Myocarditis/pericarditis	Days -365 to 0	Days 1 to 21	IP, OP

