## 7. RATIONALE AND BACKGROUND

The development of vaccines against SARS-CoV-2 has been critical to ending the Coronavirus disease 2019 (COVID-19) pandemic. In the United States (US), the first to become available were the messenger RNA (mRNA) vaccines BNT162B2 (COMIRNATY) (Pfizer Inc/BioNTech, 2023) and mRNA-1273 (Moderna US, Inc., 2023). Authorized for emergency use by the US Food and Drug Administration (FDA) on 11 December 2020 and 18 December 2020, respectively, these first-generation vaccines contained a piece of the original SARS-CoV-2 virus's mRNA, instructing cells in the body to make the virus's distinctive "spike" protein and triggering an immune response (FDA, 2020a, 2020b; Nabizadeh et al., 2023). Beginning in August 2022, in response to the new circulating Omicron variant of SARS-CoV-2, the vaccines were adapted to add an mRNA component from the Omicron lineages BA.4 and BA.5, in addition to mRNA from the original viral strain, and were thereafter referred to as bivalent vaccines (FDA, 2022b, 2022c, 2022d). In September 2023, the COMIRNATY 2023-2024 Formula was approved for individuals  $\geq 12$  years of age. The Pfizer-BioNTech COVID-19 Vaccine 2023-2024 Formula was authorized under emergency use in individuals 6 months through 11 years of age. This new formulation contains a monovalent (single) mRNA component corresponding to the Omicron variant XBB.1.5 (FDA, 2023b). The Omicron XBB sublineage accounted for nearly all COVID-19 cases in the US in spring 2023 and remained the most common variant as of 08 July 2023 (CDC, 2020).

Based on data from the original COMIRNATY formula, the US prescribing information for COMIRNATY highlights the following warnings and precautions:

- "Postmarketing data demonstrate increased risks of myocarditis and pericarditis"
- "Syncope (fainting) may occur in association with administration of injectable vaccines, including COMIRNATY." (Pfizer Inc/BioNTech, 2023)

Additionally, the following serious adverse events have been observed after immunization with the Pfizer-BioNTech, Moderna, and Janssen vaccines as reported in the Vaccine Adverse Event Reporting System (VAERS): glomerulonephritis, herpes zoster, immune-mediated myositis, and relapsing or progressing MS (VAERS, 2023). More information is needed on whether the safety profile of the COMIRNATY 2023-2024 Formula remains consistent with the safety profile of the original formula in the overall population and subpopulations of interest.

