**Table 2. Clean periods and risk intervals for safety outcomes of interest**

Outcome	Clean Period*	Vaccine Risk Interval*	Care Setting**
Pulmonary embolism	Days -365 to 0	Days 1 to 28	IP, OP
Stroke, hemorrhagic	Days -365 to 0	Days 1 to 28	IP
Stroke, ischemic	Days -365 to 0	Days 1 to 28	IP
Transverse myelitis	Days -365 to 0	Days 1 to 42	IP, ED

\*Expressed in relation to the day of vaccination or cohort entry (Day 0). When more than one vaccine risk interval had been cited in the prior literature, the present risk interval was chosen from the prior literature using the following order of priority for all outcomes other than myocarditis/pericarditis: 1) CBER 2021; 2) the most frequently cited risk interval in prior literature; and 3) the shortest risk interval cited in prior literature. The risk interval for myocarditis/pericarditis was chosen based on [CBER 2022](#).

\*\*IP, Inpatient; ED, Emergency department visit; OP, Outpatient facility claims and professional/provider claims.

\*\*\*Could not be determined from the literature, so modeled after other outcome intervals in [CBER 2021](#).

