### 9.3.2.1. Outcome-Specific Risk and Control Periods

The SCRI design ([Section 9.1.1](#)) requires that clean periods, risk intervals, washout periods, and control intervals be specified for every study outcome. The lengths of the clean periods and risk intervals are listed in [Table 2](#). The washout period for all outcomes will begin immediately after the end of the risk interval and continue for 30 days ([Akpandak et al., 2022](#)); the control period will follow the washout period and be equivalent in length to the risk interval. Interval lengths were determined based on prior vaccine literature, including COVID-19 vaccine studies conducted as part of the FDA’s Center for Biologics Evaluation and Research (CBER) Biologics Effectiveness and Safety (BEST) System ([Akpandak et al., 2022](#); [Barda et al., 2021](#); [CBER, 2021](#); [Joy et al., 2023](#); [Klein et al., 2021](#); [Liu et al., 2023](#); [Martin et al., 2021](#); [McCarthy et al., 2013](#); [Wack et al., 2021](#)).

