  - I21.3 – ST elevation (STEMI) myocardial infarction of unspecified site
  - I21.4 – Non-ST elevation (NSTEMI) myocardial infarction
  - I21.9 – Acute myocardial infarction, unspecified
  - I21.A1 – Myocardial infarction type 2
  - I21.A9 – Other myocardial infarction type
  - I22.0 – Subsequent ST elevation (STEMI) myocardial infarction of anterior wall
  - I22.1 – Subsequent ST elevation (STEMI) myocardial infarction of inferior wall
  - I22.2 – Subsequent non-ST elevation (NSTEMI) myocardial infarction
  - I22.8 – Subsequent ST elevation (STEMI) myocardial infarction of other sites
  - I22.9 – Subsequent ST elevation (STEMI) myocardial infarction of unspecified site

- Myocarditis/pericarditis\*
  - B33.22 – Viral myocarditis
  - B33.23 – Viral pericarditis
  - I30.0 – Acute nonspecific idiopathic pericarditis
  - I30.1 – Infective pericarditis
  - I30.8 – Other forms of acute pericarditis
  - I30.9 – Acute pericarditis, unspecified
  - I32 – Pericarditis in diseases classified elsewhere
  - I41 – Myocarditis in diseases classified elsewhere
  - I40.0 – Infective myocarditis
  - I40.1 – Isolated myocarditis
  - I40.8 – Other acute myocarditis
  - I40.9 – Acute myocarditis, unspecified
  - I51.4 – Myocarditis, unspecified
- Pulmonary embolism\*
  - I26.02 – Saddle embolus of pulmonary artery with acute cor pulmonale
  - I26.09 – Other pulmonary embolism with acute cor pulmonale
  - I26.92 – Saddle embolus of pulmonary artery without acute cor pulmonale
  - I26.93 – Single subsegmental pulmonary embolism without acute cor pulmonale
  - I26.94 – Multiple subsegmental pulmonary emboli without acute cor pulmonale
  - I26.99 – Other pulmonary embolism without acute cor pulmonale
- Stroke, hemorrhagic\*
  - I61.0 – Nontraumatic intracerebral hemorrhage in hemisphere, subcortical
  - I61.1 – Nontraumatic intracerebral hemorrhage in hemisphere, cortical
  - I61.2 – Nontraumatic intracerebral hemorrhage in hemisphere, unspecified
  - I61.3 – Nontraumatic intracerebral hemorrhage in brain stem
  - I61.4 – Nontraumatic intracerebral hemorrhage in cerebellum
  - I61.5 – Nontraumatic intracerebral hemorrhage, intraventricular
  - I61.6 – Nontraumatic intracerebral hemorrhage, multiple localized
  - I61.8 – Other nontraumatic intracerebral hemorrhage

- I61.9 – Nontraumatic intracerebral hemorrhage, unspecified
- I62.00 – Nontraumatic subdural hemorrhage, unspecified
- I62.01 – Nontraumatic acute subdural hemorrhage

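### Myocarditis and pericarditis are analysed only as one pooled outcome with no component results, so a 4- to 5-fold myocarditis rise could often stay below the signal rule if pericarditis predominates and is less affected

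*Protocol*

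**What the plan says.** Section 9.3.2 lists the outcomes for both the self-controlled (SCRI) and cohort analyses, and Table 2 gives their windows. Both carry a single entry, "Myocarditis/pericarditis", with clean period Days -365 to 0, risk interval Days 1 to 21, and inpatient or outpatient setting. The Table 2 footnote says "The risk interval for myocarditis/pericarditis was chosen based on" an FDA CBER source from 2022. Section 17.3 gives one joint list of 13 codes, for example "I40.9 – Acute myocarditis, unspecified" and "I30.9 – Acute pericarditis, unspecified", and any single code qualifies. Sections 9.7.1.1 and 9.7.2.2 to 9.7.2.4 plan no result for either disease alone.

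In 9.3.2, record retrieval is required in the interim report when there is a signal, defined as a "rate ratio of > 3.0 and a corresponding P value of < 0.01 in the primary analysis of the SCRI design". Review is optional for other analyses or for the final report. It is also optional below the threshold: "Medical records may also be retrieved for AESIs with estimates approaching the pre-specified safety signal threshold".

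Section 7 quotes the label warning: "Postmarketing data demonstrate increased risks of myocarditis and pericarditis". It says the study is needed to learn whether the safety profile of the new formula matches that of the original. Section 7 also calls the document a combined protocol and SAP, and Annex 1 lists no standalone documents, so the component analysis has not been deferred to another plan.

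**The concern.** Among the study outcomes, this is the one for which Section 7 quotes a label warning, and the warning names two diseases. One blended ratio cannot show which of them has changed, or whether one has changed while the other has not. Where the two ratios differ, the pooled ratio lies between them, and the threshold of 3.0 is high. A several-fold rise in the less common component could therefore appear as a modest pooled ratio that does not oblige record review.

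Elsewhere the protocol separates related conditions. Stroke is split into hemorrhagic and ischemic. The only ADEM code, G04.00, is also in the encephalomyelitis list, so a narrow outcome already sits beside a broader one that contains it.

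**Working it through.** **Inputs from the protocol.** The 13 codes in 17.3 divide into 7 for myocarditis (B33.22, I40.0, I40.1, I40.8, I40.9, I41, I51.4) and 6 for pericarditis (B33.23, I30.0, I30.1, I30.8, I30.9, I32). Section 9.3.2.1 says "the control period will follow the washout period and be equivalent in length to the risk interval", so person-time is 1:1. The signal rule is rate ratio above 3.0 with P below 0.01.

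**Assumed, because the protocol does not state them.** The myocarditis share p of background events; the expected background events per window, B; the component ratios RRm (myocarditis) and RRp (pericarditis); a two-sided exact P value; and each event belonging to one component only. The protocol gives no event count or power figure to reproduce.

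**Dilution.** Pooled RR = p × RRm + (1 − p) × RRp. With RRp = 1 this exceeds 3.0 only if RRm > 1 + 2/p:

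- p = 0.2: 1 + 2/0.2 = 11
- p = 0.3: 1 + 2/0.3 = 7.7
- p = 0.5: 1 + 2/0.5 = 5

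**Signal probability.** Take independent Poisson counts r (risk window) and c (control window). The control mean is B for the composite and pB for myocarditis alone; the risk mean is the control mean times the relevant RR. Sum the probabilities of all pairs with r/c > 3 and two-sided exact binomial P < 0.01 (success probability 1/2).

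B = 20, RRm = 5:

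| p | Separate myocarditis | Pooled, RRp = 1 | Pooled, RRp = 2 | Pooled, RRp = 3 | Pooled, RRp = 5 |
|---|---|---|---|---|---|
| 0.2 | 74% | 4% | 29% | 69% | 99% |
| 0.3 | 89% | 13% | 44% | 77% | 99% |
| 0.5 | 95% | 50% | 73% | 89% | 99% |
| 0.7 | 97% | 83% | 91% | 95% | 99% |

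B = 20, RRm = 4, RRp = 1, pooled versus separate: 2% vs 48% (p = 0.2), 6% vs 71% (p = 0.3), 25% vs 80% (p = 0.5).

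**More events.** B = 40, RRm = 5, RRp = 1: pooled falls to 0.8% (p = 0.2) and 6% (p = 0.3), while separate rises to 93% and 96%. The true pooled ratios are 0.2 × 5 + 0.8 × 1 = 1.8 and 0.3 × 5 + 0.7 × 1 = 2.2. Both are below 3.0, so added precision makes a pooled signal less likely.

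**Fewer events.** B = 5, RRm = 5, RRp = 1, pooled versus separate: 3% vs 5% (p = 0.2), 9% vs 16% (p = 0.3), 29% vs 42% (p = 0.5). With B = 2 both are at or below about 5% over that range. The rule needs at least 8 events even if all fall in the risk window: 2 × 0.5^7 = 0.016 fails and 2 × 0.5^8 = 0.008 passes.

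**False signals.** With a true ratio of 1, a single component meets the rule with probability below 0.3% at 1, 2, 5, 10 and 20 expected events per window.

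**The case against.** A reader might infer that pericarditis is unaffected and that the rule will usually miss a myocarditis rise. The protocol supports neither. Section 7 cites increased risks of both diseases, and no section says pericarditis is spared. How often the rule misses depends on p, B and both ratios, none of which is given. At p = 0.7 the pooled analysis signals 83% of the time even with RRp = 1. With RRp = 3 it signals 69% to 89% of the time for p from 0.2 to 0.5. If both ratios are 5, it reaches 99% and beats the separate myocarditis analysis. With sparse events the miss comes from the count and the threshold, which splitting does not cure; Section 9.9 itself warns of limited power, particularly in Phase 1.

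The composite also has a stated source. Section 17.3 marks its codes as based on FDA CBER BEST studies, and Table 2 ties its interval to CBER. The signal rule governs record review and not reporting, so a pooled ratio of 1.8 or 2.2 would still be published, with its confidence interval in the SCRI. Review remains possible at discretion.

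All of this stands, and it makes the composite a defensible choice. It does not supply a component result. The discretionary review is a weak safeguard here, because the protocol does not define what counts as approaching the threshold and a ratio near 2 is not obviously close to 3.0.

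**Conclusion.** The point holds as a conditional one. The plan contains no component result for the two diseases named in the label warning it quotes. If myocarditis is a minority of background events and pericarditis is less affected, a 4- to 5-fold myocarditis rise could often fall short of the rule that obliges record review. At 20 background events and myocarditis ratio 5, for shares of 0.2 to 0.5, the pooled probability is 4% to 50% with RRp = 1 and 29% to 73% with RRp = 2, against 74% to 95% for myocarditis alone. These figures rest on assumed shares, counts and ratios and on a two-sided exact test. They illustrate the possible loss and do not predict this study's performance. The protocol does not support saying that the composite is an error or that a myocarditis rise would go unreported. This is a worthwhile, inexpensive improvement to a defensible choice.

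**What to change.** Keep the composite unchanged. In 9.3.2, Table 2 and 17.3, add myocarditis (the 7 codes) and pericarditis (the 6 codes) as two further outcomes. Give them the composite's risk interval, care setting and clean period, and apply the pooled definition in the clean period so that a recent diagnosis of either disease still excludes. State how an event carrying codes from both lists is counted. Report both components in the SCRI and the cohort, and apply the signal rule to each as well as to the composite.

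The cost is two more rows per outcome table and no new codes. Each component has fewer events and so a wider interval, and there are two more comparisons, each with the small false-signal probability computed above. Retaining the composite preserves the gain from pooling when both diseases rise together.

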**Table 2. Clean periods and risk intervals for safety outcomes of interest**

Outcome	Clean Period*	Vaccine Risk Interval*	Care Setting**
Pulmonary embolism	Days -365 to 0	Days 1 to 28	IP, OP
Stroke, hemorrhagic	Days -365 to 0	Days 1 to 28	IP
Stroke, ischemic	Days -365 to 0	Days 1 to 28	IP
Transverse myelitis	Days -365 to 0	Days 1 to 42	IP, ED

\*Expressed in relation to the day of vaccination or cohort entry (Day 0). When more than one vaccine risk interval had been cited in the prior literature, the present risk interval was chosen from the prior literature using the following order of priority for all outcomes other than myocarditis/pericarditis: 1) CBER 2021; 2) the most frequently cited risk interval in prior literature; and 3) the shortest risk interval cited in prior literature. The risk interval for myocarditis/pericarditis was chosen based on [CBER 2022](#).

\*\*IP, Inpatient; ED, Emergency department visit; OP, Outpatient facility claims and professional/provider claims.

\*\*\*Could not be determined from the literature, so modeled after other outcome intervals in [CBER 2021](#).

### 9.3.2.1. Outcome-Specific Risk and Control Periods

The SCRI design ([Section 9.1.1](#)) requires that clean periods, risk intervals, washout periods, and control intervals be specified for every study outcome. The lengths of the clean periods and risk intervals are listed in [Table 2](#). The washout period for all outcomes will begin immediately after the end of the risk interval and continue for 30 days ([Akpandak et al., 2022](#)); the control period will follow the washout period and be equivalent in length to the risk interval. Interval lengths were determined based on prior vaccine literature, including COVID-19 vaccine studies conducted as part of the FDA’s Center for Biologics Evaluation and Research (CBER) Biologics Effectiveness and Safety (BEST) System ([Akpandak et al., 2022](#); [Barda et al., 2021](#); [CBER, 2021](#); [Joy et al., 2023](#); [Klein et al., 2021](#); [Liu et al., 2023](#); [Martin et al., 2021](#); [McCarthy et al., 2013](#); [Wack et al., 2021](#)).

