#### **9.5. Study Size**

The sample size achieved will depend on the number of recipients of the COMIRNATY 2023-2024 Formula in the databases. All individuals who meet the study's eligibility criteria during the study period will be included.

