## 9.7. Data Analysis

### 9.7.1. SCRI

#### 9.7.1.1. Primary Analysis

Descriptive statistics will be used to summarize the baseline characteristics of those who receive the COMIRNATY 2023-2024 Formula. Counts of each safety outcome of interest will be reported within pre-specified risk and control windows. Then, the observed incidence rates of the outcomes of interest will be estimated in the risk window and the control window. Among the individuals who experience an outcome of interest in either the risk window or the control window (but not both), an exact conditional Poisson regression model with the natural logarithm of the person-time as the offset will be used to calculate the relative incidence (rate ratio) and corresponding 95% confidence interval (CI) of the risk period relative to the control period. With the self-controlled design, whereby each individual serves as their own comparator, the analysis accounts for the factors that vary across but not within individuals (i.e., time-invariant covariates).

The results from the SCRI utilizing the Optum pre-adjudicated claims database will be presented in the interim report, while results from the SCRI utilizing the ORD will be presented in the final report.

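### The equal-length rule gives anaphylaxis a 2-day SCRI control window, so the signal rule needs at least 8 risk-window cases (two-sided) and has under about 50% power unless about 8 or more are expected

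*Protocol*

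**What the plan says.** Table 2 of the protocol sets the anaphylaxis row as "Anaphylaxis Days -30 to -1 Days 0 to 1 IP, ED". Section 9.3.2.1 adds that "The washout period for all outcomes will begin immediately after the end of the risk interval and continue for 30 days", and then that "the control period will follow the washout period and be equivalent in length to the risk interval". It attributes interval lengths to prior vaccine literature and gives no reason specific to anaphylaxis for a 2-day control.

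Section 9.7.1.1 analyses the SCRI with "an exact conditional Poisson regression model with the natural logarithm of the person-time as the offset", and reports the rate ratio with the "corresponding 95% confidence interval (CI) of the risk period relative to the control period". Section 9.3.2 defines a signal that requires medical record review, "defined as a rate ratio of > 3.0 and a corresponding P value of < 0.01 in the primary analysis of the SCRI design". It also permits, without requiring it, record retrieval when an estimate approaches that threshold.

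The protocol gives no recipient count: "The sample size achieved will depend on the number of recipients of the COMIRNATY 2023-2024 Formula in the databases" (Section 9.5). It gives no background rate for anaphylaxis, no power figure, and does not say whether the P value is one- or two-sided.

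**The concern.** In an SCRI the control window supplies the reference rate. For most outcomes here that window is three to six weeks. For anaphylaxis it is two days. The next shortest risk intervals in Table 2 are 21 days (Kawasaki disease and myocarditis/pericarditis), so anaphylaxis has less than a tenth of the reference time of any other outcome.

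With equal windows, each case is a fair coin toss under the null. A small number of cases cannot then reach P < 0.01 even if all of them fall right after vaccination. At stake is whether the trigger for mandatory record review can respond to a real excess of an acute post-vaccination reaction, and whether the reported interval is narrow enough to be informative. The SCRI carries most of the weight here: Section 9.9 makes the cohort analysis primary only for chronic outcomes, and cohort follow-up of up to one year dilutes a Day 0 to 1 effect.

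**Working it through.** The plan states no power or event count, so there is no figure of its own to reproduce.

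**Windows** (Table 2 and Section 9.3.2.1). Risk: Days 0 to 1, 2 days. Washout: Days 2 to 31, 30 days. Control: Days 32 to 33, 2 days.

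**Test** (Section 9.7.1.1). Conditional on the total number of cases, the risk-window count is Binomial(risk + control, p0) under the null, with p0 = 1/(1 + k) and k = control length / risk length. For 2 days, k = 1 and p0 = 1/2. For 28 days, k = 14 and p0 = 1/15. Two-sided P is taken as twice the upper tail. This is an assumption, made because the analysis is paired with a 95% CI.

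**Floor with no control cases:**
- 2-day control: 7 cases give 2 × 0.5^7 = 0.0156; 8 give 2 × 0.5^8 = 0.0078. The floor is 8. One-sided, 0.5^7 = 0.0078, so it is 7.
- 28-day control: 2 cases give 2 × (1/15)^2 = 0.0089. The floor is 2.

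Minimum risk-window cases meeting both RR > 3.0 and two-sided P < 0.01:

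| Control cases | 2-day control | 28-day control |
|---|---|---|
| 0 | 8 | 2 |
| 1 | 11 | 3 |
| 2 | 13 | 3 |

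**Power with almost no control cases.** This is the Poisson probability of 8 or more risk-window cases: 13% when 5 are expected, 40% at 7, 55% at 8, 78% at 10. It crosses 50% between 7.5 and 7.75. Control cases push the requirement higher.

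**Power under assumed backgrounds.** Let b be the expected background events per 2 days. Risk-window counts are Poisson(b × RR), control counts Poisson(b × k), summed over every pair that meets the rule. The range b = 0.2 to 1.0 is an assumption: 1,000,000 recipients × 2/365.25 years × 4 to 18 coded events per 100,000 person-years gives 0.22 to 0.99.

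| b | RR | Expected risk cases | 2-day control | 28-day control |
|---|---|---|---|---|
| 0.2 | 20 | 4 | 4% | 67% |
| 0.5 | 10 | 5 | 9% | 66% |
| 0.5 | 20 | 10 | 62% | 98% |
| 1.0 | 10 | 10 | 48% | 94% |
| 1.0 | 20 | 20 | 98% | >99% |

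At RR = 1 the 28-day control meets the rule about 0.2% of the time across these backgrounds.

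**Confidence interval.** With 5 risk cases and 0 control cases, the exact lower limit for the binomial proportion is 0.025^(1/5) = 0.478. With a 2-day control the RR lower limit is 0.478/0.522 = 0.92. With 7 versus 1 it is 0.90. With a 28-day control, 5 versus 7 cases (the expected counts at b = 0.5, RR 10) gives a lower limit of about 2.5.

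**The case against.** Equal windows are a valid design, and Section 9.9 already warns of limited power, particularly in Phase 1. This is a matter of efficiency, not an error or contradiction.

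A reader might infer more than the protocol supports, in three ways:

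- **That a large anaphylaxis risk would usually be missed.** This depends on recipient numbers and background rates that are not given. At 1.0 background events and RR 20, the 2-day design has 98% power. The rule is also a trigger for record review, not the only route to detection: counts, rates, RR and CI are reported regardless, estimates near the threshold may be reviewed, and the cohort also covers anaphylaxis. This objection stands. It is only partly reassuring, because the near-threshold review is optional and has no numeric definition, and the CI is itself wide.
- **That the test is weak at any threshold.** It is not. At P < 0.05 with the same RR condition, 2-day power is 85% (0.5, RR 20) and 75% (1.0, RR 10).
- **That the 8-case floor is peculiar to anaphylaxis.** It follows from the 1:1 ratio and applies to all 20 outcomes. What is peculiar is the scarcity of reference events in two days.

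Nor should the case rest on weekday balance: a 28-day control averages over weekdays but does not match those of Days 0 to 1.

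One further objection stands in part. The outcome code list in Section 17.3 includes T80.52XA, anaphylaxis due to vaccination, which is unlikely to be recorded in a control window without another vaccination. The constant background used above is therefore a simplification, and the 0.2% false-signal figure does not allow for this coding asymmetry. The asymmetry exists at either control length, but it matters more where two cases can meet the rule; the record review that a signal triggers is the safeguard.

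**Conclusion.** The point holds as a design inefficiency worth correcting. The 2-day control window follows directly from the protocol. The 8-case floor is exact given a two-sided test (7 if one-sided). The statement of under about 50% power unless about 8 or more risk-window cases are expected assumes almost no control cases, and the requirement rises if they occur. The comparisons with a 28-day control rest on assumed backgrounds of 0.2 to 1.0 events per 2 days and a constant background rate. Across the scenarios shown, the gain is largest at about 4 to 5 expected risk-window cases (4% to 67%, 9% to 66%) and almost vanishes at 20 (98% to over 99%). Reporting the RR and CI regardless does not remove the weakness: five cases against none still leaves a 95% lower limit of 0.92. Equal length is not needed for validity, because the model already carries a person-time offset.

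**What to change.** In Section 9.3.2.1, add that the control period for anaphylaxis is 28 days (Days 32 to 59). Keep the 30-day washout and the exact conditional model with the log person-time offset. State whether the P value in the signal rule is one- or two-sided. Version 3.0 is dated 18 March 2026 and the final report is planned for 30 April 2026, so if the SCRI has already been run, keep the 2-day result and report the 28-day analysis as a labelled supplementary analysis.

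The cost is more truncated control windows. In the final ORD data this is negligible: a recipient vaccinated on 31 March 2024 reaches Day 59 on 29 May 2024, against a planned end of data collection of 31 August 2025. In the interim extract, cut at 15 January 2024, it is material: a complete control window requires vaccination by 17 November 2023 (15 January minus 59 days) instead of 13 December 2023 (minus 33 days). The offset handles the truncated person-time, but the interim gain would be smaller than the figures above, which assume complete windows.
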